9.5.3. Urea Blood Sample

A 2 mL blood sample will be collected into Lithium Heparin tubes as soon as practically possible before the BAL samples.

Processing for plasma, storage and shipping procedures will be provided in the SRM or equivalent.

9.5.4. Sample Analysis

BAL and plasma analysis will be performed under the control of Platform Technology and Sciences – in Vitro/in Vivo Translation and Third Party Resourcing, GSK, the details of which will be included in the SRM OR equivalent. Concentrations of CCI15106 will be determined in plasma and BAL samples using the currently approved bioanalytical methodology. Plasma and BAL urea concentrations will be determined by Clinical Pathology, Safety Assessment, GSK. Raw data will be stored in the Good Laboratory Practices archives, GSK.

For bystander exposure, a plasma concentration of less than 0.5 ng/mL (the Limit Of Quantification of the method) represents an acceptable exposure since this is 29-fold

lower than the highest plasma concentration measured at the no effect dose level for teratogenicity in the most sensitive species (rat [Rebetol SPC, 2009]).

Once the plasma and BAL samples have been analyzed for CCI15106, any remaining plasma or BAL may be used for other compound-related metabolites analyses, microbiome analysis, or other exploratory analyses that inform the effect of the drug on the body or the disease, the results of which will be reported under a separate protocol.

9.6. Pharmacodynamics

Pharmacodynamic parameters are not evaluated in this study.

9.7. Genetics

Genetics are not evaluated in this study.

9.8. Biomarkers

Biomarkers are not evaluated in this study.

9.9. Health Economics OR Medical Resource Utilization and Health Economics

Health Economics/Medical Resource Utilization and Health Economics parameters are not evaluated in this study.

10. STATISTICAL CONSIDERATIONS

10.1. Sample Size Determination

Sample size is based on feasibility and though no formal power calculations are performed, the sample size is deemed adequate to provide a preliminary assessment of safety prior to progression to the next study.

Part 1

In Part 1, the study plans to enrol healthy participants in 3 cohorts. In Cohort A, there will be 6 participants on active and 2 on placebo, in cohort B, there will be 12 on active and 2 on placebo. In cohort C, there will be 14 subjects who will participate as bystanders and they will be associated with the dosing subjects in Cohort B on a one to one basis for the entire duration of dosing. All subjects in Cohort B will also undergo BAL.

Part 2:

In Part 2, 22 participants with COPD are planned to be enrolled. Cohort A will have 6 participants on active dose and 2 on placebo and Cohort B will have 12 participants on active and 2 on placebo. Fourteen participants (12 active and 2 placebo) enrolled in Cohort B Part 2 will also undergo BAL.

Although the sample size is not based on statistical criteria, general probabilities can be determined on the likelihood of seeing adverse events. For example, in Parts 1 and 2, in treatment groups where 6 patients will receive the active drug, if the true adverse outcome rate is 5%, the chance of seeing at least one adverse outcome at a given dose is 26%. Similarly, if the true adverse outcome rate is 20%, the chance of seeing at least one adverse outcome at a given dose is 73%. For the treatment groups with 12 subjects receiving the active treatment, if the true adverse outcome rate is 5%, the chance of seeing at least one adverse outcome at a given dose is 46%. Similarly, if the true adverse outcome rate is 20%, the chance of seeing at least one adverse outcome at a given dose is 93%. This level of predictability is deemed adequate within this Phase 1 setting prior to commencement of the next study.

10.1.1. Sample Size Sensitivity

As sample size is based on feasibility, no sample size sensitivity was performed.

10.1.2. Sample Size Re-estimation or Adjustment

No sample size re-estimation is planned.

10.2. Populations for Analyses

For purposes of analysis, the following populations are defined:

Population	Definition / Criteria	Analyses Evaluated
All Participants Screened	 Comprise of all participants who consent to participate in the clinical study. Defined separately for Part 1 and Part 2. 	
Safety	 Comprise of all participants who receive at least one dose of study treatment. This population will be based on the treatment the participant actually received. Defined separately for Part 1 (excluding Cohort C) and Part 2. 	SafetyStudy Population
Systemic Pharmacokinetic Concentration	Participants who receive at least one dose of study treatment and who undergo plasma PK sampling and have at least one postdose concentration result.	• PK
	PK samples that may be affected by protocol deviations will be reviewed by the study team to determine whether or not the sample will be excluded.	
	Defined separately for Part 1 (excluding Cohort C) and Part 2.	
Lung ELF Concentration	Participants who receive at least one dose of study treatment and who undergo BAL sampling and have postdose lung ELF CCI15106 and	• BAL

Population	Definition / Criteria	Analyses Evaluated
Population	 urea concentration result. Lung ELF samples that may be affected by protocol deviations, will be reviewed by the study team to determine whether or not the sample will be excluded. Defined separately for Part 1 and Part 2 	
Bystander Safety Population (Part 1, Cohort C)	Participants who are present at least once in the room with the participant receiving the dose.	SafetyStudy Population
Bystander PK Population (Part 1, Cohort C)	Participants who are present at least once in the room with the participant receiving the dose, undergo plasma PK sampling and have post-dose concentration result.	• PK
	PK samples that may be affected by protocol deviations will be reviewed by the study team to determine whether or not the sample will be excluded.	

10.3. Statistical Analyses

The analysis and reporting of Part 1 may be conducted prior to the completion of Part 2. For all parts, the analysis and reporting will be performed after the datasets are authorized and released for reporting.

Data will be listed and summarized according to GSK reporting standards, where applicable. Listings will be sorted by cohort, participant and time; summaries will be presented by cohort, treatment, and time.

Descriptive summaries will include n, mean, standard deviation (SD), median, minimum, and maximum, geometric mean with associated 95% confidence interval (CI), and the between-participant coefficient of variation (%CVb) for continuous variables, n and percent will be used as summary statistics for categorical variables.

Baseline or pre-dose assessment is the last available assessment prior to time of the first dose unless it is specified otherwise. If there are multiple assessments collected at the same scheduled time, the average of these assessments will be used. For tabulated safety summaries, only the scheduled assessments will be included in the summary tables.

Version 9.1 or higher of the SAS system will be used to analyze the data as well as to generate tables, figures, and listings.

Complete details will be documented in the RAP.

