4. OBJECTIVES AND ENDPOINTS

Objectives			Endpoints		
Pri	mary		·		
•	To investigate the safety and tolerability of CCI15106-IP following single and repeat escalating doses in healthy participants and participants with moderate COPD.	•	Adverse events (AEs), clinical laboratory, electrocardiogram (ECG), telemetry, spirometry, and vital signs assessments.		
•	To determine systemic PK of CCI15106 following single and repeat escalating doses of CCI15106-IP in healthy participants and participants with moderate COPD.	•	Derived systemic PK parameters of CCI15106: Single dose: area under the curve (AUC) from time zero to the time of last quantifiable concentration (AUC[0-last]), concentration at maximum (Cmax), time of maximum concentration (tmax), AUC from time zero to infinity (AUC[0- ∞]) elimination half-life (t1/2), clearance (CL/F), as data permit. Repeat dose: AUC from time zero to end of dosing interval (AUC[0- τ]) (τ =12 hours [h] for twice daily dose regimen), Cmax, tmax, elimination half-life (t1/2) as data permit.		
•	To evaluate potential inhalation exposure of bystanders to airborne CCI15106 during self-administered dosing of participants.	•	Concentration of CCI15106 in plasma of bystanders 15-20 minutes (min) after dosing (at predicted tmax) and amount of CCI15106 accumulated on filters fitted on bystander over 15 min after dosing.		
•	To evaluate the distribution and persistence of airborne CCI15106 in room air post-dosing.	•	Amount of CC15106 in room air assessed by measuring amount of CCI15106 accumulated over 20 and 60 min intervals during and immediately post-dosing on filters fitted on stationary pumps placed in the room.		
Se	condary				
•	To determine the concentration of CCI15106 in the lung of healthy participants and participants with moderate COPD following repeat dosing of CCI15106-IP.	•	Concentrations of CCI15106 in lung epithelial lining fluid (ELF) assessed by bronchoalveolar lavage (BAL).		
•	To investigate the performance of the Monodose RS01 device for the administration of CCI15106-IP in healthy participants and participants with moderate COPD.	•	Device safety and performance parameters, including medical device incidents reporting, as well as systemic PK and lung CCI15106 concentrations.		

Objectives	Endpoints		
Tertiary/Exploratory			
To assess dose proportionality of CCI15106-IP versus systemic PK parameters.	 Comparisons of doses administered and systemic PK parameters of CCI15106: AUC(0-24) or AUC(0-τ) and Cmax. 		

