9. STUDY ASSESSMENTS AND PROCEDURES

- Study procedures and their timing are summarized in the SoA (Section 2).
- Protocol waivers or exemptions are not allowed
- Immediate safety concerns should be discussed with the sponsor immediately upon occurrence or awareness to determine if the participant should continue or discontinue study treatment.
- Adherence to the study design requirements, including those specified in the SoA (Section 2), is essential and required for study conduct.
- All screening evaluations must be completed and reviewed to confirm that potential
 participants meet all eligibility criteria. The investigator will maintain a screening
 log to record details of all participants screened and to confirm eligibility or record
 reasons for screening failure, as applicable.
- Procedures conducted as part of the participant's routine clinical management (eg, blood count) and obtained before signing of ICF may be utilized for screening or baseline purposes provided the procedure met the protocol-specified criteria and was performed within the time frame defined in the SoA (Section 2).
- The maximum amount of blood collected from each participant over the duration of the study, including any extra assessments that may be required, will not exceed 500 mL.
- Repeat or unscheduled samples may be taken for safety reasons or for technical issues with the samples.
- The following time window tolerances apply to all protocol assessments:

Predose	- 60 to 0 min (- 60 to -15 min for spirometry)
0h - 4h post	- 5 / + 10 min
5h – 24h post	- 20 / + 20 min

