9.4.5. Spirometry

- Spirometry (FEV1 and FVC) will be performed at time points specified in the SoA (Section 2). Further tests should be performed, at the discretion of the investigator, if the participant has symptoms that could suggest bronchospasm.
- Spirometry manoeuvres will be conducted according to ATS/ERS 2005 spirometry standards [Miller, 2005]. The greatest FEV1 and the greatest FVC from 3 technically acceptable and reproducible manoeuvres will be recorded.
- For participants with COPD, at screening, 400 µg salbutamol will be administered 15-30 minutes prior to performing spirometry. FEV1 and FVC percent predicted values will be derived using the Global Lung Function Initiative reference values [Quanjer, 2012].

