9.4.7. Clinical Safety Laboratory Assessments

- Refer to Appendix 2 for the list of clinical laboratory tests to be performed and to the SoA (Section 2) for the timing and frequency.
- The investigator must review the laboratory report, document this review, and record any clinically relevant changes occurring during the study in the AE section of the CRF. The laboratory reports must be filed with the source documents. Clinically significant abnormal laboratory findings are those which are not associated with the underlying disease, unless judged by the investigator to be more severe than expected for the participant's condition.

- All laboratory tests with values considered clinically significantly abnormal during participation in the study or within 30±2 days after the last dose of study treatment should be repeated until the values return to normal or baseline or are no longer considered significantly abnormal by the investigator or medical monitor.
- If such values do not return to normal/baseline within a period of time judged reasonable by the investigator, the etiology should be identified and the sponsor notified.
- All protocol-required laboratory assessments, as defined in Appendix 2, must be conducted in accordance with the laboratory manual and the SoA (Section 2).

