10.3.1. Safety Analyses

All safety analyses will be based on the Safety Population.

Endpoint	Statistical Analysis Methods
Adverse events (AEs)	The proportion of participants reporting AEs will be tabulated by treatment and by cohort. AEs will also be tabulated by severity and relationship.
Clinical laboratory	Laboratory results will be included in the reporting of this study for hematology, clinical chemistry, and urinalysis. Based upon laboratory normal ranges, the laboratory test results will be categorized according to the normal range as low (below the lower limit), normal (within the normal range) and high (above the upper limit). Summary statistics for change from baseline will also be tabulated.
Electrocardiogram (ECG)	The ECG parameters of PR, QRS, QT, QTc, QTcF and HR (bpm) will be reported. Overall assessment of ECG (Investigator's judgment) will be recorded as Normal, Abnormal - Not Clinically Significant and Abnormal - Clinically Significant. Summary statistics for change from baseline will also be tabulated.
Telemetry	Overall assessment of Telemetry (Investigator's judgment) will be recorded as Normal, Abnormal - Not Clinically Significant and Abnormal - Clinically Significant.
Spirometry	% Predicted forced expiratory volume in 1 second (FEV1) and forced vital capacity (FVC) values will be tabulated for each timepoint.
Vital signs assessments	The following Vital Signs measurements will be tabulated: supine systolic and diastolic blood pressure, pulse rate, respiratory rate and temperature. Summary statistics for change from baseline will also be tabulated.
Monodose RS01 Device safety	Safety incidents reported from use of medical device will be tabulated.

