12.6. Appendix 6: Liver Safety: Required Actions and Follow-up Assessments

Phase I liver chemistry stopping criteria have been designed to assure participant safety and to evaluate liver event etiology.

Phase I liver chemistry stopping criteria and required follow up assessments

Liver Chemistry Stopping Criteria – Liver Stopping Event				
	ALT≥3xULN			
ALT-absolute	ALT-absolute If ALT≥3xULN AND bilirubin¹,² ≥ 2xULN (>35% direct bilirubin) or INR >1.5 Report as an SAE.			
	See additional Actions and Follow U	Jp A	ssessments listed below	
Required	Actions and Follow up Assessmer	nts f	ollowing Liver Stopping Event	
	Actions		Follow Up Assessments	
• Immediately	discontinue study treatment	•	Viral hepatitis serology ³	
Report the ev	ent to GSK within 24 h	•	Obtain INR and recheck with each	
Record the liver event data, and complete an SAE data collection tool if the event also meets the criteria for an SAE2			liver chemistry assessment until the transaminases values show downward trend	
Perform liver event follow up assessments		•	Blood sample for pharmacokinetic (PK) analysis, obtained within 48 h of	
Monitor the participant until liver chemistries			last dose ⁴	
resolve, stabilise, or return to within baseline (see MONITORING below)		•	Serum creatine phosphokinase (CPK) and lactate dehydrogenase (LDH).	
Do not restart or rechallenge participant with study treatment		•	Fractionate bilirubin, if total bilirubin≥2xULN	
MONITORING:			Obtain complete blood count with	
If ALT≥3xULN AND bilirubin ≥ 2xULN or INR			differential to assess eosinophilia	
>1.5 :	.h.a.vaiatriaa (inalyala ALT ACT	•	Record the appearance or worsening	
 Repeat liver chemistries (include ALT, AST, alkaline phosphatase, bilirubin) and perform liver 			of clinical symptoms of liver injury, or hypersensitivity, on the AE report form	
event follow up assessments within 24 hrs		•	Record use of concomitant	
Monitor participants twice weekly until liver chemistries resolve, stabilise or return to within baseline			medications on the concomitant medications report form including acetaminophen, herbal remedies, other over the counter medications.	
 A specialist or hepatology consultation is recommended 		•	Record alcohol use on the liver event	

If ALT≥3xULN AND bilirubin < 2xULN and INR ≤1.5:

- Repeat liver chemistries (include ALT, AST, alkaline phosphatase, bilirubin) and perform liver event follow up assessments within 24-72 hrs

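### The scheduled-assessments-only rule covers every safety table, so an extreme seen only at an unscheduled reading, above all a symptomatic FEV1 fall, can be missing from all tables of measured values

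*Protocol*

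**What the plan says.** Section 10.3 of the Protocol (latest amendment) sets the rule: "For tabulated safety summaries, only the scheduled assessments will be included in the summary tables". It gives no exception. The same section says that summaries are presented by cohort, treatment and time, that data are also listed, and that full detail goes to the reporting and analysis plan.

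The rule governs the primary safety endpoint in Section 4: "Adverse events (AEs), clinical laboratory, electrocardiogram (ECG), telemetry, spirometry, and vital signs assessments". Section 10.3.1 plans spirometry tables by timepoint, laboratory results classed as low, normal or high, and change-from-baseline statistics for laboratory, ECG and vital signs. It names no worst post-baseline summary.

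Several sections provide for readings outside the schedule:

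- Spirometry, Section 9.4.5: "Further tests should be performed, at the discretion of the investigator, if the participant has symptoms that could suggest bronchospasm".
- Laboratory, Section 9.4.7: clinically significant abnormal values "should be repeated until the values return to normal or baseline or are no longer considered significantly abnormal".
- Liver events, Section 12.6: repeat chemistry within 24 h or 24–72 h, then monitoring. In the more serious case: "Monitor participants twice weekly until liver chemistries resolve, stabilise or return to within baseline".
- ECG, Section 9.4.4: further QTc readings are foreseen.
- General, Section 9: "Repeat or unscheduled samples may be taken for safety reasons or for technical issues with the samples".

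**The concern.** Whether many of these readings exist depends on the outcome: they are taken because a participant has symptoms or an abnormal result. A rule that admits only scheduled readings answers what values looked like at routine times. It does not answer how far any participant's values moved. The first question is right for a table of means by timepoint. The second is also needed in a first study of a new inhaled formulation, where Section 3.3.1 lists bronchospasm and haemolytic anaemia among the risks and dosed cohorts have 6 or 12 active participants.

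At stake is whether the depth of an FEV1 fall, or a peak ALT, reaches a table at all. The rule is stated without limit, so a later analysis plan could not add worst-case tables that use unscheduled values without contradicting the protocol.

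**Working it through.** **The plan's own figures.** The protocol gives no figure for this point. The only safety figures in the statistics section are in Section 10.1, the chance of at least one adverse outcome, 1 − (1 − p)^n:

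- n = 6: p = 5% gives 26.5% (stated 26%); p = 20% gives 73.8% (stated 73%).
- n = 12: p = 5% gives 46.0% (stated 46%); p = 20% gives 93.1% (stated 93%).

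They reproduce to within one point. They show that the safety argument rests on seeing single events in small groups, so one participant's extreme matters.

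**Scheduled post-dose spirometry, counted from Section 2.** A dose counts as covered if the schedule places at least one spirometry reading in the 4 h after it. A pre-dose test the next morning, about 12 h after an evening dose, is not counted.

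| Cohort | Doses | Covered | Not covered |
|---|---|---|---|
| Repeat-dose cohorts (Cohort B, Parts 1 and 2) | 14 days × 2 = 28 | 5 (mornings of Days 1, 3, 6, 11, 14) | 28 − 5 = 23 |
| Cohort A Part 1 | 2 single + 14 × 2 = 30 | 7 (Days 1, 3, 6, 8, 11, 16, 19) | 30 − 7 = 23 |
| Cohort A Part 2 (single-dose COPD) | 1 | 1 (0.25, 0.5, 1 and 4 h) | 0 |

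In both multiple-dose schedules the 23 uncovered doses are all 14 evening doses plus 9 morning doses. Readings in the first hour follow only 2 of 28 doses in the repeat-dose cohorts (Days 1 and 14) and 4 of 30 in Cohort A Part 1 (Days 1, 3, 6 and 19).

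**Following a value through the tables.**

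1. *Spirometry.* A participant develops symptoms after an uncovered dose. If the investigator orders spirometry under Section 9.4.5, that reading is unscheduled. The table by timepoint omits it, and no other spirometry table is planned. The event can enter the adverse event table, but the FEV1 value is only in the listing.
2. *Liver chemistry.* A scheduled ALT at or above 3 × ULN stays in the table as high. Treatment stops, and under Section 8.1 that means withdrawal from the study. Later chemistry then falls mostly on the unscheduled follow-up of Section 12.6, so a higher peak is missing from the summary statistics although the category is unchanged.
3. *Other laboratory values.* In the repeat-dose cohorts, on-study samples after dosing starts fall on Days 7 and 15 and at follow-up. If an unscheduled safety sample between them is abnormal and the value has recovered by the next scheduled sample, the category table shows only normal results.
4. *ECG.* Scheduled 2 h readings follow 8 of 28 doses in the repeat-dose cohorts (Days 1, 3, 4, 6, 7, 8, 10, 12). A maximum QTcF at an extra reading would be left out.

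**The case against.** The strongest reply is that the sentence is ordinary data handling for nominal-time tables. It follows the rule on multiple readings at one scheduled time, summaries are by time, and detail is left to an analysis plan that is not shown. That use of the rule is sound and should stay. But the sentence names all tabulated safety summaries and carries no such limit, so it fixes the matter for the later plan.

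The second reply is that the information survives elsewhere. This stands in large part. Adverse events are tabulated by severity and relationship whatever the assessment schedule. Clinically relevant laboratory changes are entered as adverse events (Section 9.4.7). Serious liver events must be reported as SAEs (Section 12.6). Listings are not restricted and can be read by eye at this size. What remains missing is the measured extreme in any table.

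Three stronger readings are tempting, and the documents do not support them:

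- A reader might infer that worst values are routinely removed. Repeats under Section 9.4.7 follow a value already judged abnormal; if that value was scheduled, it stays.
- A reader might infer that the distortion always favours safety. Repeats run until recovery, so leaving them out also drops recovered values, and some unscheduled samples are technical (Section 9). Omitting readings can only understate an extreme, but its effect on means may go either way.
- A reader might turn 23/28 into an 82% chance that a bronchospasm goes untabulated, or (23/28)² = 67% for two. That needs equal risk after every dose, independence for the second figure, and an unscheduled test actually being done, which Section 9.4.5 leaves to discretion. Nothing in the protocol supports equal risk, and the counts describe a sparse schedule more than the effect of the rule.

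**Conclusion.** The point holds as a defect of scope. A rule that is right for nominal-time summaries is applied to every safety table, including the laboratory categories, with no worst-case summary beside it. Extremes seen only at an unscheduled reading can therefore be missing from every table of measured values.

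Its size is given by the schedule: 23 of 28 doses in the repeat-dose cohorts and 23 of 30 in Cohort A Part 1 have no scheduled post-dose spirometry, so an acute transient fall there could be measured only by an unscheduled test. The counts rest on the Section 2 tables and on the 4 h definition above. They are shares of doses, not event probabilities. The single-dose COPD cohort is not affected in this way. The laboratory case is narrower, and the data are not lost from the report. This is a worthwhile, cheap improvement and does not invalidate the safety analysis.

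**What to change.** Replace the sentence in Section 10.3 with:

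> Only scheduled assessments are used for summaries by nominal time. Unscheduled assessments, other than readings discarded and replaced for technical reasons, are included in worst-case post-baseline summaries by treatment and cohort: lowest FEV1 and FVC, laboratory category by worst post-baseline value, maximum QTcF and extreme vital signs.

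The cost is a changed sentence and a few extra tables from data already collected, with no new assessments and no change to participants' care. There is a small downside: participants with more repeats have more chances of an extreme value. A footnote giving the number of assessments per participant makes that visible.
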